15.1.2 Sub-group & interim analysis

There is no planned interim analysis for this study.

15.2 Cost effectiveness analysis

Mean differential costs between the two groups will be estimated. As cost data are often skewed, non-parametric bootstrapping methods will be used to test for differences in costs between groups [27]. (Unless one intervention is dominant (lower cost greater effect), results will be reported in the form of an incremental cost utility ratio (cost/QALY). A cost effectiveness acceptability curve will show the probability of the more costly intervention having an incremental cost utility ratio below a range of acceptability thresholds [28].

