5.2 Secondary objectives

- To compare the effectiveness of probiotics vs. placebo, taken in conjunction with antibiotics, on the duration and severity of AAD in care home SUs.
- To compare the effectiveness of the probiotics vs. placebo in reducing the incidence of *C. difficile*-associated diarrhoea (CDAD) in care home SUs.
- To evaluate *th*e impact of the probiotics on Quality of Life (QoL) in care home SUs.
- To evaluate the cost effectiveness of probiotics for AAD in care home SUs.

6 Study design

This is a phase III individually randomised, double-blinded, parallel group trial of probiotic versus placebo for care home SUs who are prescribed antibiotics for acute infection. A total of 400 SUs from approximately 24 care homes in Wales (and potentially England) will be randomised.

The target population are SUs resident in care homes under a long-term care plan. Data entry, management and analysis will be conducted centrally at the South East Wales Trials Unit (SEWTU).

7 Centre and Investigator selection

Care homes located in Wales and if necessary from the South West and other parts of England will be approached to take part in the PAAD Study. We will seek agreement about participation in the study from the manager and the owner of suitable care homes. An agreement, detailing roles and responsibilities will be signed by the care home manager and the owner of the care home. The care home manager will be defined as the Principal Investigator (PI) at the care home, as the study site, and by Cardiff University as the sponsor of the study.

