13.4.3 Quality of Life

Health-related quality of life will be assessed at the beginning of each week for the duration of the eight-week follow-up period via the EQ-5D.

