14.4 Sample size

A total of 400 SUs (200 per arm) will need to be randomised in order to achieve 80% power, at the 5% level, to detect a 50% relative reduction in the incidence of antibiotic associated diarrhoea in those given probiotic intervention alongside antibiotic treatment, compared to placebo alongside antibiotic treatment. This sample size has been adjusted for a 20% loss to follow-up/withdrawal.

Taking into consideration the results from the interim analysis performed in PAAD Stage 1 and a more recent interim assessment of antibiotic prescribing and AAD (from first antibiotic prescription), assuming an AAD incidence of 25% in the placebo arm (lower confidence limit quoted in Appendix 3), in order to randomise 400 SUs we will need to obtain advanced consent from at least 607 SUs (assuming 66% will be prescribed at least one course antibiotics during the 12 month monitoring period and subsequently randomised) and will need to approach approximately 1214 SUs in order to achieve this consent rate (assuming only 50% will provide consent). With an average of 60 SUs per home, we will need to recruit from a minimum of 21 care homes. In order to allow for care home drop-out, larger than anticipated withdrawals/drop-out/declines and smaller than anticipated care homes, we aim to recruit from 24 care homes.

15 Analysis

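### Section 15.2 defines the acceptability curve by a cost/QALY ratio lying below a threshold, which read literally counts costlier-and-worse results as acceptable (minor, secondary cost-utility analysis only)

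*Protocol*

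**What the plan says.** Cost-effectiveness is a secondary objective (protocol 5.2): "To evaluate the cost effectiveness of probiotics for AAD in care home SUs". Section 15.2 describes the analysis in a few sentences:

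- Mean cost differences are estimated, and "non-parametric bootstrapping methods will be used to test for differences in costs between groups".
- On the summary measure: "Unless one intervention is dominant (lower cost greater effect), results will be reported in the form of an incremental cost utility ratio (cost/QALY").
- On uncertainty: "A cost effectiveness acceptability curve will show the probability of the more costly intervention having an incremental cost utility ratio below a range of acceptability" (cut-off values), with a health-economics methods text as the reference.

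QALYs come from the EQ-5D over a short period (13.4.3): "Health-related quality of life will be assessed at the beginning of each week for the duration of the eight-week follow-up period via the EQ-5D".

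The protocol names no threshold, no cost or QALY standard deviation and no net-benefit statistic. It does not say how negative ratios are classified, and it attaches no decision rule to the curve.

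**The concern.** The curve is the only statement of joint cost and QALY uncertainty that the protocol describes, and its criterion is written out: ratio below threshold. That criterion is sound only when the costlier arm is also the more effective one. The two quadrants with fewer QALYs are handled wrongly. A costlier-and-worse result passes at every positive threshold. A cheaper-and-worse result passes when the saving per QALY lost is too small and fails when it is large enough.

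This trial is exposed because any QALY difference over eight weeks is likely to be small against its standard error, so the estimates will straddle zero. An analyst who followed the sentence literally would publish a curve that reads too favourably for whichever arm costs more, and a reader would take it as evidence on a stated objective.

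**Working it through.** Section 15.2 gives no figure to reproduce. The check is of the criterion itself, followed by its size under assumed inputs.

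**1. Which results each rule accepts.** Let ΔC and ΔE be the cost and QALY differences (costlier arm minus the other) and λ the threshold.

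| Result | Literal rule, ΔC/ΔE < λ | Net benefit, λΔE − ΔC > 0 |
|---|---|---|
| Cheaper, better | accepted | accepted |
| Costlier, better | accepted if ΔC < λΔE | the same |
| Costlier, worse | **always accepted** | never accepted |
| Cheaper, worse | accepted if the saving is **less** than λ per QALY lost | accepted if the saving is **more** than λ per QALY lost |

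Hence literal minus net benefit = P(costlier, worse) + P(cheaper, worse, saving too small) − P(cheaper, worse, saving sufficient).

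If the true ΔE is 0 and ΔC is independent of ΔE, the two negative-ratio quadrants together have probability 0.5. The literal value is then 0.5 + P(0 < ratio < λ), which is above 0.5 for every positive λ.

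**2. Inputs.** Protocol 14.4 gives the numbers and error rates: "A total of 400 SUs (200 per arm) will need to be randomised in order to achieve 80% power, at the 5% level, to detect" the target effect, which is a halving of AAD. It allows for attrition: "This sample size has been adjusted for a 20% loss to follow-up/withdrawal". It sets the control rate by "assuming an AAD incidence of 25% in the placebo arm". This gives 200 × 0.8 = 160 analysed per arm, and AAD of 25% against 12.5%. Assumed, because the protocol gives none of them: utility SD 0.3, so an 8-week QALY SD of 0.3 × 56/365 = 0.046; cost SD 300 to 1500; cost-QALY correlation −0.3 to +0.3; true ΔC 0 to 200; λ = 20,000 per QALY.

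**3. Is ΔE near zero?** If an AAD case costs 0.2 utility for 5 days (assumed), the full target effect is worth 0.125 × 0.2 × 5/365 = 0.0003 QALY. The standard error of ΔE is 0.046 × √(2/160) = 0.0051, about 15 times larger.

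**4. One case by hand.** Take cost SD 300, true ΔC = 100, true ΔE = 0 and correlation 0.

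- SE(ΔC) = 300 × 0.1118 = 33.5, and λ × SE(ΔE) = 20,000 × 0.00514 = 102.9.
- SD of net benefit = √(102.9² + 33.5²) = 108.2.
- Net-benefit probability = Φ(−100/108.2) = Φ(−0.92) = 0.18.
- ΔC is about 3 standard errors above zero, so nearly all positive ratios below λ are costlier-and-better. The literal value is about 0.50 + 0.18 = 0.68.
- The excess of 0.50 is the costlier-and-worse share.

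**5. Over the assumed range.** Trials were simulated with normal sampling, the costlier arm was taken from the observed means, and true ΔE was 0.

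| | Literal curve | Net benefit |
|---|---|---|
| All trials | about 0.57–0.92 | about 0.08–0.47 |
| Costlier arm not dominated on observed means | about 0.39–0.89 | about 0.14–0.67 |

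Repeat runs move the ends of these ranges by about 0.02. In the second row the literal curve was higher in every scenario, by about 0.13 to 0.26. The costlier arm was dominated on observed means in roughly 40–60% of trials.

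**6. Not always above one half.** With QALY SD 0.04, cost SD 1500, true ΔC = 100, correlation +0.3 and λ = 5,000, the literal value is about 0.45, against 0.27 for net benefit.

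**The case against.** **Shorthand.** The protocol names a standard object and cites a methods text, and probability of a ratio below a threshold is a common brief description of it. A health economist may well compute it correctly, and the treatment of replicates by quadrant is often left to an analysis plan, which is not shown here. This stands as a reason to rate the point low. It does not remove it, because the criterion is stated and, as stated, it is not a valid ordering.

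**The dominance clause.** A ratio is not reported when one arm is dominant. Where the costlier arm is truly harmful, this will usually point the right way. With true ΔE = −0.01 and ΔC = +200, placebo is cheaper and better on observed means with probability Φ(0.01/0.0051) × Φ(200/72.7) = 0.974 × 0.997 = 0.97 at cost SD 650, and 0.974 × 0.883 = 0.86 at cost SD 1500 (zero correlation). The curve alone would mislead there, but section 15.2 as a whole generally would not. The clause governs the ratio, however. The curve sentence carries no such condition, and the distortion remains, though smaller, in trials without apparent dominance.

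**Stronger readings that a reader might infer.** One is that dominance is called from point estimates alone; the protocol does not say how it is judged. Another is that the plan contains a rule favouring the costlier arm under no effect; it states no decision rule and no cut-off such as 0.5. Bootstrapping is named only for the cost comparison, so a count of bootstrap replicates behind the curve is also an inference. The ordering error does not depend on it, since it holds however the probability is computed.

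**Conclusion.** Wrong as written, minor, and confined to the secondary cost-utility analysis. The algebra in step 1 needs no assumptions: a ratio below a threshold is not a valid criterion when the QALY difference can be negative. The direction, overstated support for the costlier arm when the QALY difference is near zero, held in every scenario examined. The size rests wholly on assumed standard deviations, correlation, cost difference and threshold. Under those it is about 0.57–0.92 against 0.08–0.47 over all trials, with a smaller gap where the costlier arm is not dominated on observed means. The documents do not support saying that the literal curve always exceeds one half, that dominance is decided on point estimates, or that any conclusion follows mechanically from the curve. The primary outcome, sample size and data collection are unaffected.

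**What to change.** Replace the curve sentence in 15.2, or settle it in the health-economics analysis plan, along these lines:

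> Incremental net benefit will be calculated as λ × ΔQALY − ΔCost for probiotic versus placebo. The acceptability curve will show, at each λ, the probability that it is above zero, obtained by resampling each service user's costs and QALYs as a pair. The curve will be reported whichever quadrant the point estimates fall in, including when one arm appears dominant.

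Naming the comparison as probiotic versus placebo also removes the dependence on which arm turns out costlier, which is known only from the data.

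The cost is a change of wording. The costs and QALYs are already needed for the planned ratio, and the bootstrap planned for costs is extended to pairs; no participants, visits or forms are added. The downside is that a plain statement of dominance, or a single ratio, will be accompanied by a less favourable statement of uncertainty.

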15.3 Data storage & retention

All data will be kept for 15 years in line with Cardiff University's Research Governance Framework Regulations for clinical research. This data will be stored confidentially on password protected servers maintained on the Cardiff University Network.

Electronic data will be stored on fire-walled University computers, and only accessible to researchers involved in the study. All procedures for data storage, processing and management will be in compliance with the Data Protection Act 1998. All paper records will be stored in a locked filing cabinet, with keys available only to the trial management team. The Trial Statistician will carry out analysis. All essential documents generated by the study will be kept in the trial master file.

16 Study closure

The end of the study will be considered as the date on which the last participant has completed their follow-up assessment.

For the purpose of regulatory requirements the end of the study is defined as the end of the follow-up period of the last recruited SU. For the purpose of the research ethics committee the study end date is deemed to be the date of last data capture.

17 Regulatory and ethical issues

17.1 CTA

This clinical trial has been registered in the EudraCT database and Clinical Trials Authorisation (CTA) will be obtained from the Medicines and Healthcare products Regulatory Agency (MHRA) prior to the start of the study in accordance with Part 3, Regulation 12 of the UK Statutory Instrument.

17.2 Ethical and governance approval

The trial will be conducted in accordance with the recommendations for physicians involved in research on human participants adopted by the 18th World Medical Assembly, Helsinki 1964 and later revisions.

Research governance approval will be granted by Research and Commercial Development at Cardiff University.

This study protocol has been submitted to a Research Ethics Committee (REC) recognised by the United Kingdom Ethics Committee Authority for review and approval. A favourable ethical opinion has been obtained from the REC prior to the commencement of any trial procedures.

All substantial protocol amendments must be approved by the REC responsible for the study, in addition to approval by NHS R&D (and MHRA approval if applicable to the amendment). Minor amendments will not require prior approval by the REC.

If the study is stopped due to adverse events it will not be recommenced without reference to the REC responsible for the study.

The outcome of the study (e.g. completed) will be reported to the REC responsible for the study within 90 days of completion of the last patient's final study procedures. In the event of the study being prematurely terminated a report will be submitted to the REC responsible for the study within 15 days.

A summary of the Clinical Trial Report will be submitted to the REC responsible for the study within one year of completion of the last subject's final study procedures.

17.3 Ethical Conduct of the Study

The Chief Investigator and the Co-Investigators shall be responsible for ensuring that the clinical study is performed in accordance with the following:

- Declaration of Helsinki (Seoul, 2008; Appendix 1).
- ICH Harmonised Tripartite Guideline for Good Clinical Practice.
- The Medicines for Human Use (Clinical Trials) Regulations 2004 [26] (Statutory Instrument 2004 No. 1031) as amended by the Medicines for Human Use (Clinical Trials) Amended Regulations 2006 (Statutory Instrument 2006 No. 1928 and No. 2984) and Amended Regulations 2008 (Statutory Instrument 2008 No. 941).
- Research Governance Framework for Health and Social Care (Welsh Assembly Government 2nd Edition, September 2009 and Department of Health 2nd Edition, July 2005)

17.4 Risks and benefits for trial participants and society

The proposed study does pose ethical issues, namely the conduct of a randomised placebo controlled trial in a population with the potential challenge of mental capacity. For this reason, prior to enrolment and at randomisation, the mental capacity of all SUs will be assessed by trained CHS. In case of reduced capacity, the personal legal representative or the professional legal representative will be approached for the provision of consent.

Due to randomisation of the population involving a placebo, not all service users will receive an intervention of clinical benefit. The question to be answered by the research is whether the consumption of a probiotic during treatment with an antibiotic, effectively prevents AAD and how this impacts not only the clinical care but also the effect on cost of managing care home residents.

From the NHS perspective, the cost of treating AAD in care homes poses a substantial burden on care provided to residents and the prescription rate of antibiotics within the NHS. However it should be noted that costs to the NHS would be incurred if they require primary care, e.g., GP visits and prescriptions or admissions to hospital.

Under the current proposal by the MHRA on risk based approaches to conduction of CTIMPs, the MHRA consider this study to be an efficacy study of VSL[#]3 in a new and unlicensed indication and have defined this study to be a Type B trial, which identifies the risk to SUs as being somewhat higher than that of standard medical care.

The study medication will be delivered by appropriately trained and experienced care home- clinical staff or study trained staff, managed and monitored by SEWTU.

17.5 Confidentiality

The Chief Investigator and the research team will preserve the confidentiality of participants in accordance with the Data Protection Act 1998.

. All data will be handled according to the principles of the Data Protection Act, especially for sensitive, personal data. Data will be anonymised and stored on a password protected computer located in secure University buildings and appropriately backed up. Any data transfer will be closely monitored. A privacy risk assessment will proactively identify and ameliorate risks of breaches of confidentiality and clearly designate the named individuals who will be allowed to access identifiable information. All data will be retained for up to 15 years post study closure in line with Cardiff University's procedures.

17.6 Indemnity

Cardiff University will provide indemnity and compensation in the event of a claim by, or on behalf of participants, for negligent harm as a result of the study design and/or in respect of the protocol authors/research team. Cardiff University does not provide compensation for non-negligent harm.

17.7 Study sponsorship

This study is sponsored by Cardiff University, under the governance of the Research and Development Commercial Division. Delegated responsibilities will be assigned to the NHS trusts taking part in this study.

17.8 Funding

This study is funded by the Department of Health via the Health Technology Assessment (HTA) programme.

17.9 Audits & inspections

The study is open to inspection by HTA as the funding organisation. The study may also be participant to inspection and audit by Cardiff University under their remit as sponsor. As this study is classified as a clinical trial of investigational medicinal products (CTIMP), it may also be participant to inspection by the MHRA.

18 Study management

18.1 Internal Project Team

This group will consist of the Chief Investigators and the Trial Management Team within SEWTU and will meet at least fortnightly to discuss the day-to-day issues that arise from the study. All important discussions will be relayed to the TMG for final decision.

18.2 Trial Management Group

The TMG will consist of the Chief Investigator, Co-Applicants, a member of the CHS, a lay representative, TM, Trial Statistician and Trial Administrator. The role of the TMG will be to help set up the study by providing specialist advice, input to and comment on study procedures and documents (information sheets, protocol, etc). They will also advise on the promotion and running of the trial and deal with any issues that arise. The group will meet monthly throughout the course of the study.

18.3 TSC (Trial Steering Committee)

A TSC will be established and will meet at least 6 monthly. It will comprise an independent chair and three other independent members. This committee will provide independent oversight of the study.

The committee will be chaired by [name], Professor of Geriatric Medicine, Research Institute of Life Course Studies, Keele University, who has extensive clinical trials expertise as well as expertise in the care of the elderly.

The first meeting will be before the study commences to review the protocol and arrange the timelines for the subsequent meetings. The TSC will provide overall supervision for the trial and provide advice through its independent chair. The ultimate decision for the continuation of the trial lies with the TSC, after discussion with the TMG.

18.4 IDMC (Independent Data Monitoring Committee)

In order to monitor accumulating data on safety and any study intervention benefit, an independent data monitoring committee (IDMC) will be established. The IDMC will act as an advisory body to the TSC and will meet annually.

19 Data monitoring and quality assurance

Regular monitoring will be performed according to ICH GCP and the trial monitoring plan. Data will be evaluated for compliance with the protocol and accuracy in relation to source documents. Following written standard operating procedures, the monitors will verify that the study is conducted and data are generated, documented and reported in compliance with the protocol, GCP and the applicable regulatory requirements.

20 Publication policy

All publications and presentations relating to the study will be authorised by the TMG and will be in accordance with the study's publication policy.

21 References

 Surawicz, C.M., Probiotics, antibiotic-associated diarrhoea and Clostridium difficile diarrhoea in humans. Best Practice & Research Clinical Gastroenterology, 2003. 17(5): p. 775-783.

2. Parkes, G.C., J.D. Sanderson, and K. Whelan, *The mechanisms and efficacy of probiotics in*

the prevention of Clostridium difficile-associated diarrhoea. Lancet Infect Dis, 2009. **9**(4): p. 237-44.

3. Fletcher, K.R. and M. Cinalli, *Identification, Optimal Management, and Infection Control Measures for Clostridium difficile-Associated Disease in Long-Term Care.* Geriatric Nursing, 2007. **28**(3): p. 171-181.

4. Monaghan, T., T. Boswell, and Y.R. Mahida, *Recent advances in Clostridium difficile- associated disease.* Gut, 2008. **57**(6): p. 850-860.

5. Nelson, R., *Antibiotic treatment for clostridium difficile-associated diarrhea in adults (Review).* The Cochrane Collaboration, 2007(3).

6. Bartlett, J.G., *Antibiotic-Associated Diarrhea.* N Engl J Med, 2002. **346**(5): p. 334-339.

7. Makris, A. and S. Gelone, *Clostridium difficile in the Long-Term Care Setting.* Journal of the American Medical Directors Association, 2007. **8**(5): p. 290-299.

8. Bignardi, G.E., *Risk factors for Clostridium difficile infection.* Journal of Hospital Infection, 1998. **40**(1): p. 1-15.

9. Cunningham, R., et al., *Proton pump inhibitors as a risk factor for Clostridium difficile diarrhoea.* Journal of Hospital Infection, 2003. **54**(3): p. 243-245.

